9.3. Statistical Methods

Because this is a retrospective cohort study, we are most interested in determining whether this exposure (to hormonal contraception) is associated with our primary outcome (counting the number of pulmonary exacerbations requiring additional IV in a given year) and/or our secondary outcomes (new respiratory microbiology, liver disease/non-cirrhosis, gallstone, requiring surgery/procedure, improved BMI, incidence of VTE, osteoporosis and fragile bone fracture). Women on hormonal contraception will be compared to the primary control group of women on non-hormonal contraception. We will also compare to women on no contraception, as the secondary control group. We will exclude persons with these existing diagnosis at the start of the follow up period for outcome data (January 1, 2010). Within this objective we will be able to calculate incidence rates, relative risks and confidence intervals. We will use Poisson regression to calculate progestin-only and combined hormonal method to non-hormonal method pulmonary exacerbation rate ratios and 95% confidence intervals. This allows for adjustment of follow-up time of each individual.

(Objective 1a): We will evaluate lab values over time (ppFEV1%, serum AST, ALT, alkaline phosphatase) to determine if trends between hormonal contraceptive users and non-hormonal contraceptive users differ. See Table 5 for confounders and covariates that we will use to adjust for the primary and secondary outcomes.

We will model ppFEV1 via generalized estimating equations (GEE), allowing for correlation within a subject, and compare via a fixed effect for exposure. Among women who change or stop contraception, we will estimate and compare within-participant difference in outcomes via the model (if numbers allow). We will censor women who switch method types or become pregnant, and for 6 months post pregnancy, for the primary analysis and subsequently follow them to leverage within-patient data and analyze changes in pulmonary status and contraception. Presence of respiratory microbiology will be estimated longitudinally via GEE with a logit link function. Graphic displays and summary statistics will be used; all *p* values will be two-sided.

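### The primary Poisson model for exacerbation rates states no variance that allows for differences between women; with ordinary Poisson variance its 95% confidence intervals would be too narrow wherever rates vary beyond the Table 5 covariates

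*Combined protocol and SAP*

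**What the plan says.** Section 4.1 makes exacerbation frequency the primary objective. Section 9.3 defines the outcome as "counting the number of pulmonary exacerbations requiring additional IV in a given year", and Part VIII of the Appendix requests yearly registry totals of IV-treated episodes. The outcome is therefore a recurrent count, with several years possible per woman.

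Section 9.3 then gives the model: "We will use Poisson regression to calculate progestin-only and combined hormonal method to non-hormonal method pulmonary exacerbation rate ratios and 95% confidence intervals". The next sentence is "This allows for adjustment of follow-up time of each individual". Adjustment is covered by "See Table 5 for confounders and covariates that we will use to adjust for the primary and secondary outcomes".

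The same section does specify how repeated measurements are handled for two other outcomes: "We will model ppFEV1 via generalized estimating equations (GEE), allowing for correlation within a subject" and "Presence of respiratory microbiology will be estimated longitudinally via GEE with a logit link function". Nothing comparable is written for exacerbations. Section 7.7 also says only Poisson regression and gives no dispersion value.

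On exposure, the section says: "We will censor women who switch method types or become pregnant, and for 6 months post pregnancy, for the primary analysis".

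**The concern.** Ordinary Poisson inference assumes that, given the covariates and person-time, the variance of the count equals its mean. If some women have persistently higher rates for reasons not in the model, the variance of a woman's total exceeds its mean, and the excess grows with her follow-up. A person-time offset gets the mean right but does nothing for this.

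The direction depends on the comparison being between women. Because women who switch method are censored in the primary analysis, each woman's counted time belongs to one exposure group, so between-woman variation feeds directly into the error of the rate ratio. The planned within-participant comparison is not affected in the same way.

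Some residual variation is plausible from the plan itself. The pulmonary covariates in Table 5 include neither earlier exacerbation history, nor baseline lung function, nor centre. This makes a residual variance above zero likely but says nothing about its size.

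At stake is the main inference. A chance imbalance in frequent exacerbators across contraceptive groups could be reported as a contraceptive effect, harmful or beneficial.

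**Working it through.** **Inputs from the documents (Section 7.7).** 0.8 exacerbations per year; 575 enrolled less 15% attrition, 575 × 0.85 = 488.75 (488 used); about half on hormonal methods; two-sided alpha 0.05.

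**Assumed, because the documents are silent.** Residual between-woman variance k (variance of a woman-level rate multiplier with mean 1); follow-up per woman; an equal split of the hormonal half (244 non-hormonal, 122 combined, 122 progestin-only); covariate effects.

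**The plan's own figures.** Section 7.7 gives no interval width or dispersion, only power. A plain Poisson Wald calculation for a rate ratio of 0.70 with 244.4 women per arm for one year gives variance 1/(244.4 × 0.8) + 1/(244.4 × 0.56) = 0.01242 and SE 0.1115. Power is Φ(0.3567/0.1115 − 1.96) = 0.893, against the 80% stated. For N = 450 to 575, the same method with 15% attrition gives 0.808 to 0.893, against 0.77 to 0.86 in Table 8. The table is therefore not reproduced. That is a separate matter and does not bear on the analysis variance.

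**Closed form, no covariates.** A woman followed for t years has mean count 0.8t and variance 0.8t + k(0.8t)². Summed over a group, true variance divided by Poisson variance is

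φ = 1 + k × 0.8 × E[t²]/E[t].

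The true SE is √φ times the model-based SE, and the true error of a nominal 5% test is 2Φ(−1.96/√φ).

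| Follow-up | E[t²]/E[t] | φ, k = 0.25 | error | φ, k = 1.0 | error |
|---|---|---|---|---|---|
| 1 year, equal | 1.00 | 1.20 | 7.4% | 1.80 | 14.4% |
| 1.4 years, equal | 1.40 | 1.28 | 8.3% | 2.12 | 17.8% |
| mean 1.4 years, variable | 2.48 | 1.50 | 10.9% | 2.98 | 25.7% |
| 3 years, equal | 3.00 | 1.60 | 12.1% | 3.40 | 28.8% |
| mean 3.0 years, variable | 4.51 | 1.90 | 15.5% | 4.61 | 36.1% |
| 8 years, equal | 8.00 | 2.60 | 22.4% | 7.40 | 47.1% |

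**Simulation of the two contrasts that Section 9.3 names.** Each hormonal group was compared with non-hormonal users under no exposure effect. Administrative follow-up was uniform on 1 to 9 years, cut by exponential censoring (mean 1.5 or 5 years, floor one month), giving mean follow-up of 1.4 and 3.0 years. Two time-varying covariates were adjusted for: one continuous (log-rate effect 0.4) and modulator start (−0.5). Residual variation was gamma with variance k. There were 1,500 replicates for each of the two contrasts.

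| k | 0 | 0.1 | 0.25 | 0.5 | 1.0 |
|---|---|---|---|---|---|
| Error, mean 1.4 years | 5.5% | 7.8% | 11.6% | 17.5% | 27.8% |
| Error, mean 3.0 years | 4.9% | 9.5% | 17.1% | 26.4% | 37.3% |
| True SE / model SE, 1.4 years | 1.0 | 1.13 | 1.23 | 1.44 | 1.78 |
| True SE / model SE, 3.0 years | 1.0 | 1.18 | 1.39 | 1.76 | 2.21 |

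The errors are for annual rows with model-based variance; woman-level totals agree within 0.3 percentage points. The SE ratios come from a separate run of 3,000 replicates. Robust variance clustered on the woman gave 5.4% to 7.0% in every setting, and a negative binomial model on woman totals gave 4.7% to 5.8%. A second simulation, with 489 women, two equal groups and 1, 3 or 8 years of equal follow-up, gave 4.5% to 5.7% with robust variance.

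**The case against.** The strongest reply is that this is an unstated option and not a wrong choice. Naming Poisson regression fixes the mean model; a robust variance can be requested within the same regression, and the plan nowhere says the variance will be model-based. Sections 6.0 and 7.7 also say the analysis plan was still being refined. Both points are true and limit the severity. Neither supplies the missing specification, and an analyst following Section 9.3 as written has no instruction to depart from ordinary variance.

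The size is open to challenge. All values of k and of follow-up are assumptions, and nothing in the documents supports k = 1.0 after Table 5 adjustment. The 1.4-year scenario has very uneven follow-up; with equal follow-up of 1.4 years the errors would be 8.3% and 17.8%, not 12% and 28%. Equal follow-up of 8 years would be worse than either simulated scenario. Within-woman regularity, such as no new episode starting during an IV course, could offset part of the excess. These points stand as limits on the magnitude and do not reverse its direction where residual variation between women is material.

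The censoring sentence sits in the paragraph on ppFEV1, so its reach to exacerbations could be disputed. It refers to the primary analysis, however, and the GEE wording names only ppFEV1 and microbiology, so the ambiguity does not fill the gap.

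The negative binomial result is partly circular, because the data were generated from that model. Robust variance reached 7.0% in one setting, so it is close to nominal and not exact.

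Finally, Table 8 lies below plain Poisson power, so an unstated allowance for dispersion in planning cannot be excluded. None is documented, and it would not define the variance used in the analysis.

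**Conclusion.** The concern holds. Section 9.3 leaves the variance of the primary rate ratios unspecified while specifying GEE for two secondary outcomes. With ordinary Poisson variance the primary intervals are too narrow for any material residual variation between women. At k = 0 nothing is lost. At k = 0.25 the true error of a nominal 5% test is about 12% to 17% in the two simulated follow-up patterns, and about 7% if every woman contributes exactly one year. At k = 1.0 it is 28% to 37% in the simulated patterns. These figures rest on assumed k, follow-up, group split and covariate effects, and the documents do not show where in the range the study lies. The point estimates are not claimed to be biased. This should be fixed before analysis; confidence is medium because the size is unknown and the plan was described as still under refinement.

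**What to change.** In Section 9.3, state the analysis unit and the variance for the primary model. Either of these would do:

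- Poisson regression (or Poisson GEE) with a log person-time offset and robust variance clustered on the woman.
- A negative binomial model on woman-level totals with the same offset.

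Report the estimated dispersion with the rate ratios so that readers can see how much it mattered.

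The change is one sentence and needs no new data. The cost is wider intervals when overdispersion is present, and hence lower real power. For 489 women in two equal groups with one year each and a rate ratio of 0.70, power falls from 0.893 at k = 0 to 0.843, 0.793 and 0.700 at k = 0.25, 0.5 and 1.0. That loss is already there if the rates vary; ordinary variance only hides it.

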approved contraceptives has increased significantly since 2001, especially with the FDA-approval of hormonal longacting reversible contraceptive methods. In today's U.S. market, two types of hormonal contraceptives exist: estrogenand-progestin-containing methods (a.k.a. combined hormonal methods) and progestin-only methods. Within the estrogen-containing methods, contraceptive choices include oral pills and non-oral methods, such as the transdermal patch and vaginal ring. Within the progestin-only methods, contraceptive choices include four different hormonal intrauterine devices (IUD), a subdermal implant, a 3-month injectable depo-medroxyprogesterone acetate (DMPA), and progestin-only oral pills

The most recent edition of the national contraceptive guidance for women with medical conditions called the United States Medical Eligibility Criteria for Contraceptive Use (USMEC), was released in 2016 by the Centers for Disease Control and Prevention (CDC), which lists CF as a chronic health condition (6). The USMEC lists all hormonal methods safe to prescribe without restrictions (USMEC = 1), except the 3-month injectable, depot-medroxyprogesterone acetate (DMPA). DMPA is listed as USMEC = 2, in which the advantages of using the method in a woman with CF generally outweighs the theoretical or proven risks because of concerns about DMPA on bone health. Despite these national recommendations, the data for women with CF and hormonal contraception are limited. Potential complications for CF patients include decreased pulmonary function, CF-related diabetes (CFRD), CFLD, increased gallbladder disease, decreased nutritional status, increased venous thromboembolism and poor bone health. There are theoretical concerns that hormonal contraception may adversely impact these complications. Another concern is the reduced efficacy of hormonal contraception, specifically oral contraceptive pills with concomitant use of CFTR modulators.

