7.5. Outcomes (include DAG diagrams to show relationships between exposure and outcomes)

Table 5: Outcomes and associated confounders and covariates

Exposure of interest	Outcome	Confounders/Covariates	Rationale
Combined	Pulmonary outcomes	Smoking	Affects lung function
hormonal contraception (CHC)	 Annual pulmonary exacerbation rate (PEx) (defined as episodes requiring intravenous 	Insurance status (reflection of SES)	Will be used as socioeconomic indicator. Less access to meds may mean less
&	antibiotic use at home or in		compliance
Progestin-only	hospital)Absolute change in FEV1 (in	Age	Lung function worsens as one ages
contraception	liters) Prevalence of micro-organism (defined as 1 or greater sputum	Education (reflection of SES)	Affects contraceptive knowledge decision making
	culture within a 12-month period)P. aeruginosa	ВМІ	Associated with better or worse health status in general

Exposure of interest	Outcome	Confounders/Covariates	Rationale
	 MDR P. aeruginosa Staph aureus 	Exercise	May reduce pulmonary exacerbation rates
	MSSA MRSA	CF genotype class	Associated with severity of disease
	Secondary infections: • Burkholderia cepacia	CFTR modulator treatment	Likely preserves pulmonary decline
	 Burkholderia cenocepacia Mycobacterial species –includes M. tuberculosis and NTM species 	Comorbidity with CFRD (defined as requiring chronic insulin therapy) (11)	Associated with worse disease (reduced immunity)
		Length of hormonal contraceptive use (person-year of exposure)	
	Venous/arterial thromboembolism (VTE)	BMI ≥ 30	
	 Noted on self-respondent survey (defined as blood clot requiring anticoagulation treatment) 	Age > 35 years PMHx for thrombophilia Arterial/venous lines or ports Pmhx cancer Smoking	
	Liver outcomes	BMI	Obesity contributes to
	 Liver disease, non-cirrhosis Gallstone, requiring surgery/procedure (defined as present or absent as 	Comorbidity with diabetes	liver dysfunction Associated with worse disease (reduced immunity)
	recorded in CFFPR)	Hepatitis	Risk factor for liver dysfunction
		CF genotype class Length of hormonal contraceptive use (person-year of exposure)	
	 Serum ALT, GGT (meets criteria if hepatic transaminases and GGT levels exceed upper limit of normal on at least 3 consecutive occasions over 12-month period) (12) 		Will track meeting criteria annually over time
	CF-related diabetes		
	 Serum ogtt trends New onset insulin resistance or diabetes (defined as 		

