 - Percent predicted relative to predicted FVC
 - Predicted Value for FVC using GLI reference equations
 - Measure of FEV1
 - Percent predicted relative to predicted FEV1
 - Predicted Value for FEV1 using GLI reference equations
- Lab values encounter level
 - Alanine Aminotransferase (ALT or SGPT), IU/L
 - Fecal elastase value (microg/g of stool)
 - Alkaline phosphatase 2 hour blood glucose (mg/dL)
 - Total bilirubin, mg/dL
 - Hgb A1C value, %
 - o Liver enzymes drawn (pre-2010) Aspartate aminotransferase
 - o GGTP (gamma glutamyl transpeptidase), IU/L
 - Fasting glucose level (mg/dL)
 - OGTT Fasting glucose level (mg/dL)
 - Lab values summarized by calendar year
 - Fasting glucose level (mg/dL)
 - OGTT fasting glucose level (mg/dL)
 - 2-hour blood glucose (mg/dL)
- Screening tests
 - Liver function tests performed
 - o DEXA scan for bone density performed in the reporting year
 - DEXA scan result is normal

- DEXA scan result is osteopenia
- DEXA scan result is osteoporosis
- DEXA scan result is other
- DEXA scan result is unknown

V. MICROBIOLOGY

- Bacteria encounter level
 - Was bacterial culture done?
 - Date of bacterial culture [PHI]
 - Culture results
 - Staphylococcus aureus
 - o MRSA
 - o Any Burkholderia Complex species
 - Multidrug-Resistant P. aeruginosa (MDR-PA) Infection
 - Stenotrophomonas
 - o MSSA
 - Pseudomonas aeruginosa found in the culture
 - Mucoid Pseudomonas aeruginosa
 - Non-mucoid Pseudomonas aeruginosa
 - Mucoid Pseudomonas aeruginosa status unknown
- Mycobacteria encounter level
 - Was mycobacterial culture done?
 - Date of myco culture [PHI]
 - o Myco culture results
 - Mycobacterial tuberculosis
 - Mycobacterium terrae
 - Mycobacterium other
 - Mycobacterium abscessus/chelonae
 - Mycobacterium avium complex
 - Mycobacterium fortuitum group
 - o Mycobacterium gordonae
 - Mycobacterium kansasii

VI. TREATMENTS

•

- Antibiotics encounter level
 - o Chronic oral macrolide antibiotic
 - o Azithromycin
 - o Clarithromycin
 - o Sulfa
 - o Amoxicillin
 - o Tetracycline
 - o Other oral antibiotic
 - o Other chronic oral antibiotic
 - o Quinolone
 - Cephalosporin
- CFTR modulators encounter level
 - On Ivacaftor medication (VX-770)
 - VX770 (Ivacaftor) dosage
 - Ivacaftor/Lumacaftor (i.e., Orkambi)
 - Ivacaftor/Lumacaftor (i.e., Orkambi) dosage
- Other treatments encounter level

- Patient is taking enzymes
- CF-specific vitamins (i.e. vitamins A, D, E and K)
- o **Exercise**
- Other treatments annual

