 - Was the patient started on treatment for NTM

VII. COMPLICATIONS

- CF related diabetes encounter level
 - o CFRD Status
 - Chronic renal insufficiency
 - Chronic renal failure requiring dialysis
- Liver disease encounter level
 - o Gall stones
 - Gall stones, requiring surgery/procedure
 - Liver disease, cirrhosis
 - Acute hepatitis
 - Acute hepatitis infectious
 - Acute hepatitis non-infectious
 - Acute hepatitis unknown
 - Liver disease, non-cirrhosis
 - Hepatic Steatosis
 - Liver disease, other Acute liver failure
 - Other complications encounter level
 - Bone fracture
 - o Osteopenia
 - Osteoporosis
 - Cancer confirmed by histology

VIII. CARE EPISODES (HOSPITALIZATIONS/HOME IV)

- Care episodes
 - Start date for care episode [PHI]
 - End date for care episode [PHI]
 - # home IV nights with reason pulmonary exacerbation
 - # hospitalization nights with reason pulmonary exacerbation
- Care episodes summarized by calendar year
 - Total # pulmonary exacerbations treated by IV antibiotics
 - # nights in hospital for pulmonary exacerbations
 - # nights on home IV for pulmonary exacerbations
 - o Total # pulmonary exacerbation treated by IV antibiotics (incl unknown)
 - # nights hospital for pulmonary exacerbation (incl unknown)
 - o # nights home IV for pulmonary exacerbation (incl unknown)

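### The pulmonary adjustment set holds only indirect severity markers, so the primary exacerbation rate ratio can carry lung-disease differences that predate the method

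*Combined protocol and SAP*

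**What the plan says.** Section 9.3 compares combined and progestin-only users with non-hormonal users by Poisson regression on the exacerbation rate. For adjustment it refers elsewhere: "See Table 5 for confounders and covariates that we will use to adjust for the primary and secondary outcomes".

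The pulmonary block of Table 5 (7.5) lists smoking, insurance, age, education, BMI, exercise, CF genotype class, CFTR modulator treatment, CF-related diabetes (CFRD) and length of hormonal use. Genotype class is justified as "Associated with severity of disease". Exacerbations and FEV1 appear in that block only as outcomes. No other section adds a baseline lung value, a prior exacerbation count or a propensity score. The heading of 7.5 mentions DAG diagrams; none is in the available text, so any diagram could not be checked.

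Section 8.1 forms the groups by the woman's choice of contraception. Section 9.3 censors women who switch method type or become pregnant in the primary analysis. It plans a within-participant comparison for women who change or stop, provided there are enough of them.

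The Appendix requests, at encounter level, "Percent predicted relative to predicted FEV1" and, by calendar year, "Total # pulmonary exacerbations treated by IV antibiotics". It also requests start and end dates of care episodes. Registry data run from 2010; the survey asks about method use back to 2008 (9.1).

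**The concern.** Past exacerbations and current lung function are the most direct record of how severe a woman's lung disease was before she used a method. If the groups differ on them at the start, an unadjusted part of that difference enters the primary rate ratio as if the method had caused it.

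The Background gives a reason to take this seriously. It names decreased pulmonary function among the complications of CF and then says: "There are theoretical concerns that hormonal contraception may adversely impact these complications". A woman or her clinician who shares that concern could weigh lung status when choosing. The hypothesis in 3.0 is worded causally (estrogen-containing methods reduce exacerbations), so a reader will take the ratio as an effect of the method.

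**Working it through.** The documents give no figure for confounding, so there is none to reproduce. The rate ratio of 0.70 in 7.7 serves only as a yardstick.

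**Step 1. What is adjusted for, and what could be.**

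| Severity information | In Table 5 pulmonary set? | In registry request? |
|---|---|---|
| Genotype class, BMI, CFRD, modulator use | Yes, but not fixed in time before the method starts | Yes (modulators also in the survey) |
| ppFEV1 before the method | No (FEV1 is an outcome only) | Yes, encounter level |
| IV-treated exacerbations before the method | No (outcome only) | Yes, yearly counts and dated episodes |

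**Step 2. Possible size.** The documents give no severity mix, so all inputs here are assumed. Let a share p1 of hormonal users and p0 of controls have more severe disease, with R times the exacerbation rate. With a true ratio of 1.0 and no adjustment for severity:

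apparent ratio = (1 + p1(R − 1)) / (1 + p0(R − 1))

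| p1 | p0 | R = 2 | R = 3 |
|---|---|---|---|
| 0.20 | 0.30 | 1.2/1.3 = 0.92 | 1.4/1.6 = 0.875 |
| 0.20 | 0.40 | 1.2/1.4 = 0.86 | 1.4/1.8 = 0.78 |
| 0.30 | 0.20 | 1.3/1.2 = 1.08 | 1.6/1.4 = 1.14 |

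The range is 0.78 to 1.14, on both sides of 1.

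**Step 3. What that would do to the test.** From 7.7: 575 × 0.85 = 489 women after attrition, about half hormonal (244.5 per group), 0.8 exacerbations per year in controls, alpha 0.05. One person-year per woman is assumed, because 7.7 gives no follow-up time. The chance of a significant result when the true ratio is 1.0 and the apparent ratio is b is

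Φ( |ln b| / √(1/(244.5 × 0.8 × b) + 1/(244.5 × 0.8)) − 1.96 )

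- b = 0.78 (1.4/1.8): 0.251/0.108 − 1.96 = 0.37, giving about 64%.
- b = 0.86 (1.2/1.4): 0.154/0.105 − 1.96 = −0.50, giving about 31%.

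The nominal rate is 5%. Under the same model, longer follow-up shrinks the standard error but leaves the bias in place.

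**Step 4. Which women can have a true pre-method value.** Outcome follow-up starts on 1 January 2010 (9.3) and registry data also start in 2010. A full 12-month look-back therefore exists only for episodes starting in 2011 or later. For a woman already on her method on 1 January 2010, any 2010 value is measured on the method, and under the present follow-up start her 2010 exacerbations are also part of the outcome. Never-users have no method start at all. Some starts may be known only as age at first use (Table 10).

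**The case against.** Four arguments favor the plan.

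- **No documented selection by lung status.** Section 8.1 speaks of the woman's choice. The Background reports national guidance that places no restriction on hormonal methods in CF except for the injectable, and there because of bone health. This stands: a link between method choice and lung disease is plausible, not shown.
- **Severity is partly covered.** BMI, CFRD, genotype class and modulator use each carry severity information, and adjusting for them would be expected to shrink the bias. This stands, and it makes the range in Step 2 a figure before that adjustment. But none of the four is the woman's own lung function or exacerbation history.
- **Women serve as their own controls in a later analysis.** That would remove stable differences between women. It covers only those who change or stop, depends on numbers, and is not the primary ratio, from which switchers are censored. It is a partial safeguard.
- **Other pulmonary outcomes are less exposed.** Table 5 takes change in FEV1 and 9.3 looks at trends, so a difference in starting level matters less. For new microbiology, 9.3 excludes women with existing diagnoses on 1 January 2010. This stands, and the point is therefore confined to the primary exacerbation analysis. The same exclusion sets no baseline for a recurrent event rate such as exacerbations.

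**Conclusion.** The omission is certain: the set that 9.3 applies has indirect severity markers but no pre-method ppFEV1 and no prior IV-treated exacerbation count. The primary rate ratio is thus open to confounding that data already requested could reduce. Direction and size are unknown. The range 0.78 to 1.14 for a true ratio of 1.0 rests on assumed severity mixes and on no adjustment for the proxies.

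A reader might infer more than this, in three ways that the documents do not support:

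- That healthier women are offered or prescribed hormonal methods, so that a protective result would be an artifact. Nothing in the documents shows lung status guiding method choice, and the assumed mixes give bias in either direction.
- That the analysis ignores severity. It does not; it measures it indirectly.
- That confounding alone would produce the planned effect of 0.70. No scenario in Step 2 does. It would take, for example, 20% versus 50% severe at three times the rate (1.4/2.0 = 0.70), a wider imbalance than assumed there, and again before adjustment for the proxies.

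**What to change.** Amend Table 5 and 9.3 before analysis, for the primary exacerbation outcome:

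1. **Episodes starting in 2011 or later.** Add (a) the last ppFEV1 before the episode starts and (b) the number of IV-treated exacerbations in the preceding 12 months. For controls on a non-hormonal method, the episode start is the start of that method.
2. **Women already on their method when registry data begin, and never-users.** Use 2010 only as a baseline year and count outcome follow-up from 1 January 2011, so that no 2010 exacerbation is both covariate and outcome. Episodes that start during 2010 lack a full look-back and can be handled the same way.
3. **Prevalent users.** State that their baseline values are on-method and may absorb part of an effect. Repeat the primary analysis in women whose method started after the baseline year.
4. **Starts known only as age at first use.** Take the baseline from the last registry year that certainly precedes the start.
5. **Change in FEV1.** Do not carry baseline ppFEV1 adjustment over automatically; in a non-randomized comparison that is a debated choice. Compare slopes instead, through an exposure-by-time term.

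The cost is SAP wording and two derived variables, with no new data collection. One year of follow-up is lost for prevalent users and never-users, and the repeat analysis will be less precise.

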Exposure of interest	Outcome	Confounders/Covariates	Rationale
	present or absent as		
	recorded in CFFPR)		
	Nutritional status	CF genotype class	
	Change in BMI	CF-specific vitamins (Fat soluable A, D and E) (defined as	
		present or absent as recorded in CFFPR)	
		Taking any pancreatic enzyme replacement therapy (noted under medications in CFFPR)	
		CFTR modulator use (will stratify by type of modulator)	
	Bone outcomes	Length of oral steroid use	Contributes to bone
	Osteoporosis, fragile bone	(person-months of use)	weakening
	fracture	Comorbidity with pancreatic insufficiency	Reduced Vit D/Calcium absorption
		Exercise	Help prevents osteoporosis
		Age	Known risk factor for osteoporosis
		BMI	Reduced BMI is a risk factor for osteoporosis
		CF genotype class	
		Length of hormonal	1
		contraceptive use (person-year	
		of exposure)	
		Smoking	Known risk factor for osteoporosis

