8.0. Methods: Assignment of interventions

8.1. Allocation

Participants will belong to a group based on their choice of contraception. Women with CF will be allocated to hormonal group (intervention), non-hormonal groups (control), and never used contraception.

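### Age is missing from the Table 5 adjustment lists for liver disease/gallstones and for change in BMI, so these hormonal versus non-hormonal comparisons are left open to confounding by age

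*Combined protocol and SAP*

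**What the plan says.** Section 9.3 sets the main contrast: "Women on hormonal contraception will be compared to the primary control group of women on non-hormonal contraception". Women on no contraception form a secondary control group. The secondary outcomes it names include "liver disease/non-cirrhosis, gallstone, requiring surgery/procedure, improved BMI, incidence of VTE". For adjustment it points to one place: "See Table 5 for confounders and covariates that we will use to adjust for the primary and secondary outcomes".

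Table 5 (Section 7.5) gives a separate covariate list for each outcome:

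- **Pulmonary:** age is listed, with the rationale "Lung function worsens as one ages".
- **Thromboembolism:** age is listed, dichotomised at 35 years.
- **Bone:** age is listed as a known risk factor.
- **Liver disease and gallstones:** BMI, diabetes, hepatitis, then "CF genotype class Length of hormonal contraceptive use (person-year of exposure"). Age is not listed.
- **Nutritional status (change in BMI):** genotype class, "CF-specific vitamins (Fat soluable A, D and E) (defined as" present or absent in the registry), pancreatic enzymes, and "CFTR modulator use (will stratify by type of modulator"). Age is not listed.

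Section 8.1 describes how the groups arise: "Participants will belong to a group based on their choice of contraception".

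**The concern.** This is a non-randomised comparison in women aged 18 to 45 at enrollment, with outcome follow-up from 1 January 2010. The plan treats age as a confounder for three outcomes in this same cohort and leaves it out for two others, without giving a reason. If age differs between method groups and also affects the outcome, a model fitted from the stated list attributes part of the age effect to the contraceptive method.

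Both rows carry hypotheses in Section 3.0: that estrogen-containing oral methods raise gallbladder disease and liver enzymes, and that both hormonal types improve BMI. For the safety question, bias in one direction could mask a harm, and bias in the other could suggest a harm that is not there.

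**Working it through.** The plan states no figure on this point, so there is none to reproduce. The check has four parts.

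**1. Is age really absent, or implied?** The lists are specific to each row. BMI, genotype class and length of hormonal use are written out again from row to row, and age itself appears in three rows. Age in the pulmonary row therefore cannot be read as carrying over. In the liver row, each rationale (obesity, diabetes, hepatitis) matches a listed covariate, so no stray rationale suggests that an age entry was lost.

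**2. Does anything else deal with age?**

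- No matching, weighting, propensity score, age stratification or general age-adjustment statement appears.
- Excluding diagnoses present on 1 January 2010 does not balance age.
- Length of hormonal use is part of the exposure and is zero for non-hormonal users, so it does not stand in for age.
- The within-participant comparison in Section 9.3 is conditional on numbers and does not remove ageing over time.

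The age range is wide. Section 7.0 expects pre-testing to end in July 2020, which puts enrollment at about 2020-2021. Women aged 18 to 45 then were between 18 − 11 = 7 and 45 − 10 = 35 years old at the start of 2010.

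**3. How large could the effect be for liver disease and gallstones?** All inputs here are assumptions. With a true rate ratio of 1, a log-linear age effect of r per decade and a mean age gap of g years, the crude rate ratio is r^(−g/10) if hormonal users are younger and r^(+g/10) if they are older.

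| r per decade | gap 3 years | gap 5 years | gap 7 years |
|---|---|---|---|
| 1.3 | 0.92 or 1.08 | 0.88 or 1.14 | 0.83 or 1.20 |
| 1.5 | 0.89 or 1.13 | 0.82 or 1.22 | 0.75 or 1.33 |
| 2.0 | 0.81 or 1.23 | 0.71 or 1.41 | 0.62 or 1.62 |

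The central case is 1.5^(−0.5) = 0.82 or 1.5^(0.5) = 1.22. In the first direction a true rate ratio of 1.22 would look null (1.22 × 0.82 = 1.00). In the second, a null effect would look like 1.22.

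A second form uses the planned age split in Table 3: 192/(383 + 192) = 192/575 = 33.4% aged 36-45. With equal groups, the bias factor is [1 + p_H(R − 1)]/[1 + p_N(R − 1)]. Here p_H and p_N are the shares aged 36-45 among hormonal and non-hormonal users, and R is the assumed risk ratio for older versus younger women.

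| p_H vs p_N | R = 1.5 | R = 2 | R = 3 |
|---|---|---|---|
| 30% vs 36.7% | 0.97 | 0.95 | 0.92 |
| 25% vs 41.7% | 0.93 | 0.88 | 0.82 |
| 20% vs 46.7% | 0.89 | 0.82 | 0.72 |

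Swapping the groups inverts these values. The extremes become 1.1835/1.15 = 1.03 and 1.934/1.4 = 1.38.

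**4. Change in BMI.** Suppose BMI rises by s per year at every age and follow-up is T years in both groups. The expected change is then s × T in each group, and an age gap produces no bias. Bias needs one of two things:

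- a slope that varies with age, giving a spurious difference of T × (s_H − s_N), where s_H and s_N are the mean age-driven slopes in the two groups; or
- unequal follow-up, giving s × (T_H − T_N).

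Multiplying a slope by the age gap would give a bias in BMI level, which is not the Table 5 outcome, so it is not used here.

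**The case against.** The strongest reply is that an omitted covariate is not yet a confounder. Confounding needs age to differ by method and to affect the outcome, and the documents show neither for these two rows. A reader might infer that the comparisons are in fact confounded, and in particular that hormonal users are younger (because sterilization is chosen later in life), so that harm is hidden. The documents do not support that. Table 10 records sterilizing procedures under surgical history but gives no age at use, and the background says only that pills and condoms are the most reported methods. The bias could run the other way, and it could differ again against the secondary control group. This objection stands, and it limits the claim to an open risk of unknown direction.

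Three further objections stand in part:

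- The figures describe crude ratios, while the planned liver model adjusts for BMI, diabetes and other covariates that may carry some of the age effect. How much is unknown.
- A reader might extend the point to the liver-enzyme (ALT/GGT) and CF-related diabetes entries. Their covariate cells are blank in the text available, possibly because merged cells were broken in extraction, so no omission can be claimed there.
- Section 6.0 says the analysis plan would be refined during the pilot, so Table 5 may not be final. That leaves room to add age but does not add it.

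The DAG diagrams mentioned in the heading of Section 7.5 are not in the text. Section 9.3 takes its adjustment from Table 5, however, and not from a diagram.

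**Conclusion.** The omission is clear in the text. Followed as written, the plan compares liver disease/gallstones and change in BMI between self-selected groups without adjusting for age, although it adjusts for age elsewhere in the same table. These comparisons are left open to confounding by age.

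The size cannot be established from the documents. Under assumed gaps of 3 to 7 years and 1.3- to 2.0-fold risk per decade, a crude null rate ratio would lie at 0.62-0.92 or 1.08-1.62, depending on which group is older. The listed covariates may reduce this. For change in BMI, the risk depends on non-linear trajectories or unequal follow-up. Non-linearity is a reasonable worry when follow-up may begin as early as about age 7, but the documents give no BMI trajectory from which to size it.

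The point concerns secondary outcomes only. The primary outcome, exacerbation rate, and FEV1 already have age in their list.

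**What to change.** Add age to the liver disease/gallstone and nutritional-status rows of Table 5, as a continuous variable and time-updated where the model allows. Alternatively, add one sentence to Section 9.3 stating that all comparative outcome models adjust for age. That sentence would also cover the entries whose covariate cells cannot be read. A flexible form such as a spline is worth considering for BMI, but the repair does not depend on it.

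The Appendix already requests date of birth and encounter age from the registry, so no new data are needed. The cost is a line of text and one or two model terms, and no sample size or power figure changes. Making the change before the linked data are analysed avoids adding age after results are seen.
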